6.7 Early Discontinuation from the Study

Subjects must discontinue investigational product and withdraw from the study for any of the following reasons:

- Withdrawal of informed consent (subject's decision to withdraw for any reason)
- Loss of ability to freely provide consent through imprisonment or involuntary incarceration
- Any clinical AE, laboratory abnormality or intercurrent illness which, in the opinion of the investigator or sponsor, indicates that continued participation in the study is not in the best interest of the subject
- Pregnancy
- Termination of the study by Biohaven Pharmaceuticals

All subjects who terminate early (e.g., AE discontinuation) should still comply with remaining study visits and procedures as outlined in [Table 1](#), and Section [4.3.6.2](#). The only exception to this requirement is when a subject withdraws consent for all study procedures or loses the ability to consent freely (as defined above).

6.8 Lost to Follow Up

A participant will be considered lost to follow-up if he or she repeatedly fails to return for scheduled visits and is unable to be contacted by the study site.

The following actions must be taken if a participant fails to return to the clinic for a required study visit:

- The site must attempt to contact the participant and reschedule the missed visit as soon as possible and counsel the participant on the importance of maintaining the assigned visit schedule and ascertain whether or not the participant wishes to and/or should continue in the study.

- Before a participant is deemed lost to follow up, the investigator or designee must make every effort to regain contact with the participant (where possible, 3 telephone calls and, if necessary, a certified letter to the participant's last known mailing address or local equivalent methods). These contact attempts should be documented in the participant's medical record.
- Should the participant continue to be unreachable, he/she will be considered to have withdrawn from the study.

7 STUDY DRUG MANAGEMENT

7.1 Description of Study Drug

7.1.1 *Investigational Product*

An IP is defined as follows:

- A pharmaceutical form of an active substance or placebo being tested or used as a reference in a clinical study, including products already with a marketing authorization but used or assembled (formulated or packaged) in a way different from the authorized form, or used for an unauthorized indication, or when used to gain further information about the authorized form.

The IP should be stored in a secure area according to local regulations. It is the responsibility of the investigator to ensure that IP is only dispensed to study subjects. The IP must be dispensed only from official study sites by authorized personnel according to local regulations.

In this protocol, IP is/are:

- Zavegeptant 10 mg IN and will be provided as single use disposable Aptar UDS devices fully prepared and ready for administration
- Matching placebo IN devices provided as single use disposable Aptar UDS devices fully prepared and ready for administration

7.1.2 *Non-Investigational Product*

Other medications used as support or rescue medication for preventative, diagnostic, or therapeutic reasons, as components of the standard of care for a given diagnosis, may be considered as non-investigational products.

In this protocol, non-investigational product(s) is/are:

Not Applicable

7.1.3 *Formulation*

Zavegeptant (BHV-3500), is formulated as 10 mg IN for intranasal single dose administration using an Aptar Unit Dose System (UDS) liquid spray device

7.1.4 Packaging, Shipment and Storage

The product storage manager should ensure that the study drug is stored in accordance with the environmental conditions (temperature, light, and humidity) as determined by the sponsor. Please see the IB for specific conditions. If concerns regarding the quality or appearance of the study drug arise, do not dispense the study drug and contact the Sponsor/Clinical Research Organization (CRO) immediately.

7.2 Dose and Administration

Subjects who are hospitalized will be administered three doses (IN devices) per day of blinded IP (10 mg or matching placebo) to be dosed approximately 8 hours (+/- 2 hours) apart, for up to 14 days (42 doses) of treatment. When possible, if subjects are discharged from the hospital to another acute care medical facility prior to completing treatment, they will be provided with enough of their blinded IP and dosing instructions to continue their Q8h regimen until 42 doses have been completed.

Subjects who are discharged to home prior to completing treatment will be discontinued from study drug. Procedures indicated in Section 4.3.3.2 should be followed.

7.2.1 Method of Assigning Subject Identification

Randomization will be done through an IWRS, that will be accessed by the unblinded research pharmacists or their designees. The randomization scheme will be stratified by age (<60, 2, 60).

Initially, after informed consent is obtained at the Screening Visit, the Investigator or designee will enter the subject into the study and assign a patient ID (PID). The PIDs will be sequentially assigned within each site, and will have the format XXX-YYYY, where XXX is the 3 digit site number and YYYY is the sequential subject number.

Sites will be responsible for recording the container numbers dispensed to the subject on the Drug Accountability Form provided in the Regulatory Binder, as well as ensure appropriate documentation of dispensation in the subject's medical record.

7.2.2 Selection and Timing of Dose and Administration

Subjects, study staff, or hospital floor staff will be instructed to administer one spray from a single device three times per day at approximately 8 hours (+/- 2 hours) apart between doses. If possible, alternate nostrils should be used for each subsequent dose. Dosing will continue for up to 14 days (42 doses). For the purposes of this protocol, the start of Visit Day 1 will start when the 1st dose of study drug is administered until 24 hours later. Therefore, depending on what time the 1st dose of study drug is administered, a visit day may spread over 2 calendar days. The last dose of study drug could be administered on Visit Day 14 but could actually occur on calendar day 15 of the study.

7.3 Blinding and Unblinding

Blinding is critical to the integrity of this clinical study. However, in the event of a medical emergency or pregnancy in an individual subject, in which knowledge of the investigational product is critical to the subject's management, the blind for that subject may be broken by the treating physician.

Before breaking the blind of an individual subject's treatment, the Investigator should have determined that the information is necessary, (i.e., that it will alter the subject's immediate management). In many cases, particularly when the emergency is clearly not investigational product related, the problem may be properly managed by assuming that the subject is receiving active product without the need for unblinding.

A pharmacokineticist, unblinded site monitor, unblinded site pharmacist, Biohaven Drug Supply Coordinator and pharmacovigilance designees may be unblinded before data are unblinded for the primary endpoint and all subjects complete the study. Except as noted above, other members of the BHV research team will remain blinded. For purposes of the DMC, periodic analysis will be carried out by the unblinded safety biostatistics team independent and firewalled from the team directly involved with the design and primary analysis of the trial. A report will be prepared for the DMC as outlined in the DMC charter.

In cases of accidental unblinding, contact the Medical Monitor and ensure every attempt is made to preserve the blind for remaining site personnel.

7.4 Treatment Compliance

Responsible study personnel or hospital floor staff will dispense the study drug to the study subjects. Accountability and compliance verification should be documented in the subject's study records. For subjects discharged to another care facility, treatment compliance and drug accountability should be continued.

Missed doses should be documented in the subject source/medical record. Since this study is intended to take place in the hospital setting, it is imperative that missed doses are correctly accounted for in addition to any intentional or unintentional dosing errors.

7.5 Destruction and Return of Study Drug

All unused study drug can be sent back to the drug depot for destruction only after being inspected and reconciled by the responsible Study monitor or the sponsor's designee. If it is site policy to destroy study drug on site, it is the Investigator's responsibility to ensure that arrangements have been made for the disposal, procedures for proper disposal have been established according to the applicable regulations, guidelines and institutional procedures, and appropriate records of the disposal have been documented. The unused study drugs can only be destroyed after being inspected and reconciled by the responsible Study Monitor or the Sponsor's designee.

8 ADVERSE EVENTS

An AE is defined as any new untoward medical occurrence or worsening of a pre-existing medical condition in a subject or clinical investigation subject administered an investigational (medicinal) product and that does not necessarily have a causal relationship with this treatment. An AE can therefore be any unfavorable and unintended sign (including an abnormal laboratory finding for example) symptom, or disease temporally associated with the use of the investigational product, whether or not considered related to the investigational product.

Adverse events can be spontaneously reported or elicited during an open-ended questioning, examination, or evaluation of a subject. In order to prevent reporting bias, subjects should not be questioned regarding the specific occurrence of one or more AEs.

If a specific diagnosis or syndrome is identified by the Investigator, this should be recorded as the AE, rather than recording (as separate AEs) the individual signs/symptoms or clinically significant laboratory test abnormalities known to be associated with and considered by the Investigator to be a component of the disease/syndrome.

Note: For this study, all admissions and discharges to and from the ICU need to be captured on the Adverse Event eCRF.

8.1 Definition of Terms Related to all Adverse Events (Serious and Non-serious)

Mild: Is usually transient and may require only minimal treatment or therapeutic intervention. The event does not generally interfere with usual activities of daily living.

Moderate: Is usually alleviated with additional specific therapeutic intervention. The event interferes with usual activities of daily living, causing discomfort but poses no significant or permanent risk of harm to the subject.

Severe: Interrupts usual activities of daily living, significantly affects clinical status, or may require intensive therapeutic intervention.

Life threatening: An AE is life threatening if the subject was at immediate risk of death from the event as it occurred; i.e., it does not include a reaction that if it had occurred in a more serious form might have caused death. For example, drug induced hepatitis that resolved without evidence of hepatic failure would not be considered life threatening even though drug induced hepatitis can be fatal.

Hospitalization: AEs requiring hospitalization should be considered SAEs. Hospitalization for elective surgery or routine clinical procedures that are not the result of AE (e.g., elective surgery for a pre-existing condition that has not worsened) need not be considered AEs or SAEs. If anything, untoward is reported during the procedure, that occurrence must be reported as an AE, either 'serious' or 'non-serious' according to the usual criteria.

8.2 Assessment for Determining Relationship of AE to Study Drug

The relatedness of each AE to study drug must be classified based on medical judgement and according to the following categories. The definitions are as follows:

Related: This category applies to AEs that are considered, with a high degree of certainty, to be related to the study drug. An AE may be considered related when it follows a temporal sequence from the administration of study drug, it cannot reasonably be explained by the known characteristics of the subject's clinical state, environment, or toxic factors, or other modes of therapy administered to the subject. An AE may be considered related when it follows a known pattern of response to the study drug, or if the AE reappears upon re-challenge.

Possibly related (non-serious AEs only): This category applies to AEs that are considered to have an unlikely connection to study drug, but a relationship cannot be ruled out with certainty.

Unlikely related (non-serious AEs only): This category applies to AEs that do not follow a reasonable temporal sequence from the administration of the study drug. The AE may readily have been produced by the subject's clinical state, environmental or toxic factors, or other modes of therapy administered to the subject.

Unrelated: This category applies to AEs that are considered with a high degree of certainty to be due only to extraneous causes (e.g. subject's clinical state, environment, toxic factors, disease under study, etc.) and does not meet the criteria of other categories above.

There are two types of adverse events, Serious Adverse Events (SAE) and Non-Serious Adverse Events (AEs).

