8.3.2 Collection and Reporting Serious Adverse Events

Following the subject's written consent to participate in the study, all SAEs, whether related or not related to study drug, must be collected, including those thought to be associated with protocol-specific procedures. All SAEs must be collected that occur from signing consent and throughout the course of the study up to and including the Post-dose Follow-up Visit Day 60.

All SAEs should be followed to resolution or stabilization.

An SAE report should be completed for any event where doubt exists regarding its status of seriousness.

If the investigator believes that an SAE is not related to the study drug but is potentially related to the conditions of the study (such as a withdrawal of previous therapy or a complication related to study procedure), the relationship should be specified in the narrative section of the SAE Report Form.

SAEs, whether related or not related to study drug, overdose (see Section 8.3.3), potential drug induced liver injury (see Section 8.3.3) and pregnancies (see Section 8.3.4) must be reported within 24 hours of the Investigator becoming aware of the event. The Investigator is responsible for submitting all applicable events to the IRB as per the IRB's reporting requirements. Additionally, the Investigator, or designated staff, is responsible for entering the SAE information into the eCRF and/or system (i.e., event term, start/stop dates, causality, and severity).

Any serious adverse event must be reported immediately or no later than 24 hours after awareness of the event to PPD Pharmacovigilance (PVG). A written description of any serious adverse event, using the PPD SAE report form, must be sent to PPD PVG by facsimile (fax), within 24 hours after awareness of the event:

- North America: [name]
- EU EMEA: [contact]

Due to COVID-19 restrictions for sites, SAE reports may be sent via encrypted email to PPD at: [contact]. The subject line of the email must include **"Biohaven Protocol BHV3500-203."**

If a form is unable to be submitted within 24 hours, the SAE may be reported by telephone via the Safety Hotline Number:

- North America: [name]
- EU EMEA: [contact]

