9.3.6 Analysis of Safety

The investigators determine the intensity of AEs and the relationship of AEs to study therapy. The investigators' terms are coded and grouped by system organ class using the latest version of the Medical Dictionary for Regulatory Activities (MedDRA) available. AEs are presented by system organ class and preferred term in descending order of overall frequency of events. If a subject had an AE with different intensities over time, then only the greatest intensity is reported.

Deaths, all AEs, and SAEs are listed for the enrolled analysis set.

The frequencies of the following safety events on study are summarized by treatment group and overall for the safety analysis set: SAEs; AEs by intensity and overall; treatment-emergent AEs by intensity and overall; AEs leading to study drug discontinuation; and treatment-emergent AEs by relationship to study drug.

Clinically significant laboratory test abnormalities on study will be identified as Grade 3 to 4 laboratory test results graded according to numeric laboratory test criteria in CTCAE Version 5.0 (2017), if available. Otherwise, if CTCAE grades are not available, then results will be graded

according to numeric laboratory test criteria in Division of AIDS (DAIDS) Table for Grading the Severity of Adult and Pediatric Adverse Events Corrected Version 2.1 (2017). If a subject has a laboratory test abnormality with different toxicity grades over time, then only the highest toxicity grade will be reported.

Further safety analyses will be described in the SAP.

9.3.7 *Futility Analysis*

A formal futility analysis will be performed by the DMC statistician after approximately 50% of subjects complete the 14-day treatment period.

The DMC will test for futility stopping only. This test will not be counted against the alpha spend for the study. In particular, zavegeptant will be tested for inferiority to placebo, on the primary endpoint (the six point, ordinal, severity scale). This will be done using a Wilcoxon rank sum test at a one-sided alpha level of 0.05.

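### Section 8.2 leaves SAEs only Related and Unrelated, each needing high certainty, so an SAE of uncertain cause has no valid causality category

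*Protocol*

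**What the plan says.** Section 8.2 makes classification compulsory: "The relatedness of each AE to study drug must be classified based on medical judgement and according to the following categories". It then defines four categories.

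- "Related: This category applies to AEs that are considered, with a high degree of certainty, to be related to the study drug". Two further sentences say when an event may be placed here: a temporal sequence with no other reasonable explanation, a known response pattern, or recurrence on re-challenge.
- "Possibly related (non-serious AEs only): This category applies to AEs that are considered to have an unlikely connection to study drug", although the relationship cannot be excluded with certainty.
- "Unlikely related (non-serious AEs only): This category applies to AEs that do not follow a reasonable temporal sequence" from dosing, and that other causes may readily have produced.
- "Unrelated: This category applies to AEs that are considered with a high degree of certainty to be due only to extraneous causes", with the added condition "and does not meet the criteria of other categories above".

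Section 8.3.2 speaks of SAEs in two levels only: "all SAEs, whether related or not related to study drug, must be collected". It also makes causality one of the items the site must enter for each SAE, and it requires a follow-up report within 24 hours if the relationship of an ongoing SAE changes. Section 9.3.6 lists among its summaries by treatment group "treatment-emergent AEs by relationship to study drug".

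**The concern.** A two-level causality scale for SAEs is workable when one threshold divides all cases. Here the scale has two thresholds, one at each end, and the space between them has been removed for serious events. An investigator who thinks a serious event might be drug-related, but is not nearly sure either way, must enter a code and has none whose definition the event meets. Two investigators with the same evidence could choose opposite codes, and neither could be queried against the protocol.

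What is at stake is whether the SAE causality field means the same thing from case to case and from site to site, and so whether the by-relationship table and individual case attributions can be interpreted.

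**Working it through.** No arithmetic beyond a count applies, so the definitions are set side by side.

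| Category (Section 8.2) | Open to SAEs? | What it requires |
|---|---|---|
| Related | Yes | High certainty that the drug is responsible |
| Possibly related | No | Unlikely connection, not excluded with certainty |
| Unlikely related | No | No reasonable temporal sequence; other causes may readily explain it |
| Unrelated | Yes | High certainty that only extraneous causes are responsible, and no other category met |

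**Step 1: count.** Four categories, less two restricted to non-serious events, leaves two for SAEs. Both require high certainty, so the number available to an SAE of uncertain cause is 2 − 2 = 0.

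**Step 2: is Unrelated a residual category?** No. Its closing condition is added to its certainty test and does not replace it. An event that fails Related does not thereby become Unrelated.

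**Step 3: is there a rule elsewhere?** Sections 8.3.1 to 8.3.5, 8.4 and 9.3.6 give no default or tie-break. The narrative instruction in Section 8.3.2 covers an SAE judged unrelated to drug but linked to study conditions. It does not cover doubt about the drug itself.

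**Step 4: does the protocol itself foresee such SAEs?** Four situations follow from its own text.

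1. Potential drug-induced liver injury (Section 8.3.5) must be reported as an SAE when no other cause is immediately apparent. Having no obvious alternative at first report falls short of high certainty, in either direction.
2. Section 4.3.3.2 and Table 1 warn of possible rebound after withdrawal of an immunomodulating agent. If rebound resembled worsening of the underlying illness, the clinical state could reasonably explain it, which defeats the first route to Related. Nor could the investigator be nearly sure that only extraneous causes were at work.
3. ICU admission or intubation for worsening counts as an SAE under Section 8.3.1. Where competing causes exist, the same problem arises.
4. Under Section 8.4.1 a non-serious AE that becomes serious is reported as an SAE. If it was coded Possibly related, that code is no longer allowed, although the evidence on cause may not have changed.

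**Step 5: the middle definitions.** Possibly related rests on an unlikely connection, and the next category is named Unlikely related. The two differ in part, because only the latter turns on timing. Still, an event with reasonable timing and a plausible but unproven drug link is more than an unlikely connection and less than highly certain. No definition describes it, whether the event is serious or not.

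**Step 6: where the code is used.** It is entered for each SAE, a change in it triggers a follow-up report, and it feeds the by-relationship table. That table takes in serious events, since Section 8.2 treats SAEs and non-serious events as the two types of adverse event.

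**The case against.** The strongest reply has four parts.

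- **Judgement.** Section 8.2 refers to medical judgement, and its sentences on when an event may be considered related give some room. But judgement is to be exercised according to the categories. Those sentences sit under the high-certainty definition and need either no other reasonable explanation, a known pattern or re-challenge. They do not cover plausible competing causes.
- **Deliberate design.** The two-level scale looks intended: the restriction is stated twice and Section 8.3.2 uses matching language. This stands. The defect is that the two definitions are not exhaustive, so two levels can be kept.
- **Little depends on the code.** This largely stands. SAEs are collected and reported within 24 hours whatever their relationship. Section 9.3.6 summarises SAEs by arm, and Section 3.2.2 counts deaths, SAEs and severe AEs, without regard to cause. The discontinuation rules in Sections 6.6 and 6.7 are not tied to the causality code.
- **The overlap is a separate matter.** The similarity of Possibly and Unlikely related bears directly on non-serious events. That is correct, and it is reported here as a second fault in the same definitions, not as support for the first.

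A reader might go further and infer that doubtful SAEs will drift to Unrelated and hide a signal from the DMC. The documents do not support this. Unrelated has its own demanding test, so an investigator could as readily choose Related. Section 10.2 has the DMC review safety by treatment group, fully unblinded on request, and describes no review confined to drug-related SAEs.

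**Conclusion.** The point holds as a definitional error. An SAE of uncertain cause satisfies neither category open to it, and a plausible but unproven link is not described by any of the four. The consequence is inconsistent or arbitrary SAE causality codes, unreliable case-level attribution and a by-relationship table that is hard to interpret. The randomised comparison of SAEs between arms is unaffected.

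The number of SAEs concerned cannot be derived. A reader might suppose that it is most of them, because ICU admission and intubation for worsening count as SAEs. The protocol does not show this: Section 8.2 names the disease under study and the subject's clinical state as extraneous causes, so some of these events can properly be Unrelated.

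The conclusion rests on reading the Section 8.2 definitions as written, and on the SAE form offering the same choices. The form is not shown.

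**What to change.** In Section 8.2, make the SAE categories exhaustive in one of two ways:

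- keep two levels split at a single threshold, with Related meaning a reasonable possibility of a causal relationship and Unrelated meaning no reasonable possibility; or
- delete the restriction to non-serious events, so that all four categories apply to SAEs.

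Under either option, redefine Possibly related as a reasonable possibility of a causal relationship that cannot be ruled out, so that it is distinct from Unlikely related.

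The cost is an amendment to the protocol text and, if its choices mirror Section 8.2, to the SAE form. Slightly more SAEs would be counted as related. As the protocol is already at Version 7.0, SAEs coded under the present definitions would need review, or the causality data would mix two standards.
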